The studies will be conducted at UVA and will require IRB approval prior to the initiation of the trial. Thirty-six subjects with Type 1 Diabetes Mellitus will be needed to complete the protocol.

Based on our experience with similar studies, we estimate an expected 20-30% screen failures, dropouts, or withdrawals (7 to 10 subjects at UVA); thus we intend to set a recruiting target of 45 subjects. One pilot subject will be enrolled to test system performance. More than one subject may be admitted at one time.

Specific Aim 1 (SA1): Hypoglycemic risk, Open vs. Closed Loop (exercise)

Specific Aim 2 (SA2): Time within target range, Open vs. Closed Loop control during the day

Specific Aim 3 (SA3): Time within target range at night

Specific Aim 4 (Substudy/exploratory): Assess the effect size of Control Modules 1+3 (SSM+BRM) preventing nocturnal hypoglycemia and increasing time within target (80-140mg/dl) overnight as compared to CGM-augmented pump alone.

The testing of the three specific aims of the main study (SA1, SA2, SA3) involves different periods of time as presented in Figure 3. Thus, in addition to complete data, availability of partial data would allow testing some of the study hypotheses. As a general rule, a session will be considered useful for data analysis if the subject completes more than 80% of the active study protocol (29 out of 36 hours for the experimental session). Sessions completing less than 80% of the protocol will be rescheduled. Specifically, comparing risk and occurrence of hypoglycemia during the 5-hour periods encompassing exercise (14:00-19:00) on open- vs. closed-loop control will address SA1. Comparing the time within target range (70-180mg/dl) during the day (7:00-23:00) on open- vs. advisory control will address SA2, and comparing the time within target range (80-140mg/dl) and the risk for hypoglycemia overnight will address SA3 (Figure 2).

To determine sample size we used power analysis based on data from our previous closed-loop control studies, which showed significant reduction in hypoglycemia (due to Module 1) and increase in time within target during the day and overnight [15]. With N=36 subjects, the power for proving SA1 is 97% and the power for SA3 is similar, while the power for SA2 is lower, but sufficient - 85%. The significance level was reduced to $p=0.01$ to account for multiple comparisons.

[figure not shown]

Figure 2: Experimental vs. Control sessions

D. Study Duration

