In the unlikely event of a disruption in 911 phone service, the Charlottesville-UVA-Albemarle Emergency Communications Center can be reached via their non-emergency number [contact]. This number feeds into their main call area where 911 dispatchers are available 24/7.

J. ENDPOINTS

This study is an early feasibility study that will test the efficacy of DiAs - a *smart-phone-based system* compared to CGM-enhanced insulin pump treatment in an outpatient setting. Specifically, the main study will have randomized cross-over design with each patient participating in two study weeks: 1) experimental involving 5 days of data collection followed by 2 days of AAA control using insulin pump and available CGM (however, treatment based on CGM will be discouraged) and 2) Control week involving 5 days of data collection followed by 2 structured days of study at home. This series of sessions will provide data for the regulatory approval of the AAA system and for its deployment in a longer-term trial of AAA at home. In addition, the data will be used to estimate the effect size of the AAA vs. CGM-enhanced insulin pump treatment in an outpatient setting.

The *basic unit for most analyses is the glucose trace of an individual*, i.e. a time-stamped series of CGM data recorded for each person. Summary characteristics and group-level analyses are derived after the individual traces are processed to produce meaningful individual markers of average glycemia and glucose variation. The following primary endpoints will be assessed:

- Risk for hypoglycemia as measured by the Low BG Index associated with exercise (SA1);
- Time spent within 70-180 mg/dl during the day (SA2);
- Risk for hypoglycemia overnight and time spent within the target range of 80-140 mg/dl overnight (SA3).

In addition, the following secondary endpoints will be assessed:

- Extent postprandial glucose excursions during the day;
- Overall number and extent of hypoglycemic episodes;
- System reliability, including failure rates of system components, frequency analysis of lost or inaccurate CGM records, percent time of active control, and inter-device connections between DiAs and the CGM and between DiAs and the insulin pump;
- System functionality, including the DiAs GUI in terms of patient comfort with operating the system, and
- The DiAs remote monitoring by medical personnel/technicians to confirm appropriate functioning outside of the hospital setting.

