The specific aim SA4 of the Substudy is exploratory – no significant results are expected, but we will assess the effect size of Control Modules 1+3 (SSM+BRM) preventing nocturnal hypoglycemia and increasing time within target (80-140mg/dl) overnight as compared to CGM-augmented pump alone.

K. SUCCESS CRITERIA / GOAL

We hypothesize that, compared to CGM-augmented insulin pump treatment, AAA control will result in moderate effect size of approximately 0.3-0.5 in terms of:

- Prevention of hypoglycemia during and following exercise more efficiently than state-of-the-art care based on CGM and insulin pump;
- Increased time within the target range of 70-180 mg/dl during the day;
- Prevention of nocturnal hypoglycemia and increase of the time within target range (80-140mg/dl) overnight.

As a general rule, a session will be considered useful for data analysis if the subject completes more than 80% of the active study protocol (29 out of 36 hours for the experimental session). Sessions completing less than 80% of the protocol will be rescheduled.

L. STATISTICAL ANALYSIS PLAN

The testing of the three specific aims of the main study involves different periods of time as presented in Figure 2. Thus, in addition to complete data, availability of partial data would allow testing some of the study hypotheses. Measures of time within target range, risk and occurrence of hypoglycemia, glucose variability and system stability will be computed as previously described and will be accompanied by appropriate plots [20]. Repeated measures ANOVA with contrasts will be used to compare the different study periods on the basis of these measures. Specifically:

- Comparing risk and occurrence of hypoglycemia during the 5-hour periods encompassing exercise (14:00-19:00) on open- vs. closed-loop control will address SA1;
- Comparing the time within target range (70-180mg/dl) during the day (7:00-23:00) on open- vs. advisory control will address SA2, and
- Comparing the time within target range (80-140mg/dl) and the risk for hypoglycemia overnight will address SA3 (see Figure 2).

II. INFORMED CONSENT

The Pilot Consent, the Informed Consent, and the Care Partner Consent are presented in Appendix A-8.

III. PATIENT CASE REPORT FORMS

Patient Case Report Forms are presented in Appendix A-9.

IV. INVESTIGATOR AGREEMENT FORMS

Investigators Agreements Forms are presented in Appendix A-10.

V. MONITORING INFORMATION

Data and Safety Monitoring Plan

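### Holm at a 5% family-wise level would reject everything the flat 0.01 rejects, and lifts SA2 power from 85% to about 95% if the other primary endpoints have their planned effects

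*Combined protocol and SAP*

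**What the plan says.** Section C (Sample Size and Investigational Sites) sets the sample size: "Thirty-six subjects with Type 1 Diabetes Mellitus will be needed to complete the protocol". On power it states "With N=36 subjects, the power for proving SA1 is 97% and the power for SA3 is similar", and the sentence continues "while the power for SA2 is lower, but sufficient - 85" per cent. The paragraph closes with "The significance level was reduced to $p=0.01$ to account for multiple comparisons". That is the only statement on multiplicity. The number of comparisons, the family-wise level, the procedure and the sidedness are not given.

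Section J (Endpoints) has three primary bullets. SA1 is the Low BG Index around exercise. SA2 is daytime in 70-180 mg/dl. SA3 holds two measures in one bullet: "Risk for hypoglycemia overnight and time spent within the target range of 80-140 mg/dl overnight (SA3"). That makes four primary endpoints.

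Section L (Statistical Analysis Plan) names repeated measures ANOVA with contrasts. For SA1 it compares both the risk and the occurrence of hypoglycaemia, as section C does. It gives no significance level and no multiplicity rule.

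**The concern.** A single fixed threshold is a valid way to control family-wise error, but it does not relax once some hypotheses have been rejected. A step-down procedure does relax, and it keeps the usual 5% control under any dependence between the tests. If the flat 0.01 is carried into the analysis, the trial may fail to reject endpoints that Holm would reject at the conventional family-wise level. The endpoint most exposed is SA2, which the plan itself ranks as its weakest on power. Because section L is silent, the analyst also has no written rule saying which tests share the error rate.

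**Working it through.** **Inputs.** N = 36 completers, per-test level 0.01, and powers of 97% (SA1), 97% (both SA3 endpoints, reading the plan's description of SA3 power as the same figure) and 85% (SA2), all from section C. The comparison is paired because "the main study will have randomized cross-over design with each patient participating in two study weeks" (section J). Assumed, because not stated: two-sided tests, stated powers computed at 0.01, normally distributed paired differences, and a correlation between endpoints of 0, 0.3 or 0.6.

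**1. The plan's own power figures.** They cannot be reproduced. Section C says "To determine sample size we used power analysis based on data from our previous closed-loop control studies" but prints no difference, SD or within-subject correlation. Working backwards with a paired t test (35 df, two-sided 0.01), 85% needs a standardised paired effect of 0.63 and 97% needs 0.78. The steps below take the stated powers as given.

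**2. Error spent by the flat rule.** Four tests: bound 4 × 0.01 = 0.04; if independent, 1 − 0.99^4 = 0.0394. Bonferroni at 5% would allow 0.05/4 = 0.0125 per test. Five tests (SA1 risk and occurrence, SA2, two for SA3): 0.05/5 = 0.01, exactly the plan's figure.

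**3. Does Holm reject everything the flat rule rejects?** Holm compares the ordered p-values with 0.05/4 = 0.0125, 0.05/3 = 0.0167, 0.05/2 = 0.025 and 0.05. If k of the p-values are at or below 0.01, they are the k smallest, and each lies below its threshold because the lowest threshold is 0.0125. Holm therefore rejects all k and may go on. With five tests the first threshold is 0.01, so the argument still works. With six it is 0.05/6 = 0.0083 and the argument fails. Simulation agrees: no violations with four or five tests, some with six.

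**4. Size of the gain.** Four paired t tests, N = 36, 60,000 simulated trials per scenario. Ranges cover the three correlations.

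| Scenario | Endpoint | Flat 0.01 | Holm 5% |
|---|---|---|---|
| Stated powers hold for all four | SA2 | 85% | 95.2-95.9% |
| Stated powers hold for all four | SA1, SA3 (each) | 97% | 98.9-99.4% |
| Only SA2 has an effect | SA2 | 85% | about 87% |
| Paired effect 0.3 on all four | each | 19-20% | 25-27% |
| Paired effect 0.4 on all four | each | 39% | 50% |
| Paired effect 0.5 on all four | each | 61% | 74-77% |

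As a ceiling, even an unadjusted 0.05 test would add only 10.8 points for SA2 and 2.5 for SA1 at the stated powers. Holm comes close to this because the other three endpoints are nearly always rejected first.

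**5. What the gain costs in type I error.** With all four endpoints null and independent, the chance of any false rejection goes from 0.040 to 0.049. If one endpoint is null and the other three have their stated powers, its false-rejection rate goes from 1% to 4.4-4.7%. Both stay within 5%.

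**The case against.** The strongest reply is that nothing here is wrong. A single-step level is valid and simple, and it gives simultaneous intervals directly. That suits an early feasibility study whose stated uses include estimating an effect size. The 0.01 may also be only a planning level: the sentence closes a power paragraph, and planning at a Bonferroni-type level is compatible with analysing by Holm later. Both points stand. They make this an improvement rather than a defect, but they do not explain why section L gives no rule at all.

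A reader might also infer four stronger things that the documents do not support.

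- That 0.01 is too strict whatever the family. With the five comparisons that sections C and L can be read to describe, it is exactly Bonferroni. Section J favours four, since its SA1 bullet names only the Low BG Index and the overall number of hypoglycaemic episodes is a secondary endpoint, but the plan never says.
- That Holm recovers 10 to 15 points of power across the board. At the stated powers only SA2 gains about 10; SA1 and SA3 gain about 2. Gains of 11 to 15 points on every endpoint need paired effects of 0.4-0.5 on all four, where flat power is 39-61%, not the stated 85-97%.
- That the change is free. Step 5 shows that it spends error the flat rule leaves unused.
- That the trial is already short of power. Section K says "AAA control will result in moderate effect size of approximately 0.3-0.5 in terms of" several outcomes, but does not define the SD behind the effect size. On the paired scale, 0.3-0.5 gives 19.5-61.1%. On a between-subject SD, the paired effect is 0.5/√(2(1−ρ)). An assumed ρ of 0.7 gives 0.65 and 86.7% power; 0.8 gives 0.79 and 97.4%. The stated powers are therefore not shown to be wrong.

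**Conclusion.** The point holds as a low-cost improvement. For four primary endpoints, or five, Holm at a two-sided family-wise 5% level rejects everything a flat 0.01 rejects and sometimes more. This part is arithmetic and needs no assumption about effects, correlation or the analysis model. The size of the gain does depend on assumptions. If the stated powers are right for all four endpoints, SA2 goes from 85% to about 95-96%, and SA1 and SA3 from 97% to about 99%. If only SA2 has an effect, it gains about 2 points. In exchange the family-wise bound rises from 4% to 5% with four tests, and the false-rejection rate of a single null endpoint can rise from 1% to nearly 5%. The figures rest on the assumptions listed under the inputs. The dominance would be lost if the family grew to six or more tests.

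**What to change.** In section C, and again in section L, name the four primary endpoints of section J as the family, replace the flat 0.01 with Holm at a two-sided family-wise 5% level, and say that adjusted p-values will be reported. State whether SA1 occurrence belongs to the family; if it does, Holm starts at 0.01 over five tests and the advice is unchanged. The sample size need not change, since the powers quoted at 0.01 become conservative.

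The cost is about one sentence in each section, plus the added type I error described above. Confidence intervals that match Holm decisions are less simple than single-step ones. A workable choice is to report Bonferroni intervals at 1 − 0.05/4 = 98.75% for estimation, noting that they can occasionally disagree with a Holm rejection. If the sponsor prefers to keep the flat 0.01, section L should still state the family, the level and the procedure.

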At the end of the 5 day collection period, subjects randomized to the experimental session first will proceed as described in "Procedures During the Experimental Session." For those subjects who were randomized to the control session first, they will proceed as described in "Procedures During the Control Session." These two 40-hour periods will complete the 7 day study week (5 days data collection + 2 day experimental or control session). Selected subjects who are participating in the Substudy will follow "Procedures During the Substudy".

4. Procedures During the Experimental Session (Days 5-7)

EXPERIMENTAL SESSION DAY 5:

1. The study subject will perform a final upload of CGM, SMBG and insulin pump information on the evening prior to the session. If the subject is unable to do so then we will ask them to come earlier on the day of session (Day 5 of data collection period) for the study team to download the information at the office. If a subject does not provide the download until the day of session, a delay of up to 2 hours on the start time of the session may be required.
2. The subject will meet the study team and check in to the CDT Research House at 18:00.
3. The subject will be asked to perform a fingerstick using the study glucometer shortly after arrival. SMBG needs to be between 80-249 mg/dL prior to initiation of AAA control and glucose not expected to be <70 within two hours of initiation of AAA. AAA control may be delayed up to two hours until these conditions are met.
4. The study team will confirm that the subject brought his/her insulin, insulin pump supplies, and regular medications. The study team will also confirm the absence of a febrile illness and absence of acetaminophen use while wearing the CGM sensor. If all criteria are not met, the subject will be rescheduled.

5. Female subjects of childbearing potential will perform urine pregnancy test. If positive, the subject will discontinue study participation. The subject will be asked to seek confirmation of the test and the appropriate medical care.
6. The subject will be instructed that all fingersticks should be preceded by hand washing with warm water and a dry towel. The subject will be instructed to obtain fingerstick, avoiding alternative sites, when obtaining blood values. The first drop of blood will be discarded. The second hanging drop will be used to measure the glucose level.

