9. The Safety Supervision Module (SSM) will be running through the remainder of the trial (approximately 19:00 on the day of session until 7:00 on the day of discharge).
10. Dinner will be provided between 19:00 and 20:30. Dinner will consist of prepackaged meals and carbohydrate estimation will be determined by the subject.
11. Carbohydrate information and fingerstick values will be entered into the DiAs by the subject prior to the meal as described under Meal and Snack boluses.
12. Premeal insulin suggested by the DiAs will be confirmed by the subject.
13. At 23:00, DiAs will detune the AM module. The SSM and the BRM will continue to run overnight and is responsible for lowering the basal rate or insulin delivery to avoid hypoglycemia (SSM) or augmenting basal rate to compensate for changes in insulin sensitivity overnight, e.g. dawn phenomenon (BRM).
14. At approximately 23:00, lights will be turned out, and the subject will be encouraged to sleep.
15. The staff will be checking the readings of the secondary CGM receiver at 03:00AM and 05:00AM during the night; Additional readings may be taken as necessary.
16. Remote monitoring of the subject will be active all night.

Meal Times During the Study:

- Breakfast (07:00 – 08:00); Lunch (12:00 – 13:00); Dinner (19:00 – 20:30); optional snack (22:00 – 23:00). Subjects will be permitted to snack between scheduled meals.
- Snacks will not be permitted overnight (11 PM – 7 AM).
- Meals and snacks will be prepackaged meals purchased by the study team and will be brought in to the study site.
- Meals and snacks eaten during the experimental session will need to be exactly the same during the control session at home and should occur at the same time each day. This will be discussed with the study subject prior to the session.
- Study subject will determine the carbohydrate estimation for each meal. Subjects will be asked to use the same carbohydrate information for those meals and snacks for insulin dosing.

Meal and Snack Boluses:

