2. A fingerstick value will be obtained upon waking while the subject is still fasting.
3. At 7:00 AM, DiAs will activate the Advisory Module (AM). The AM will be active from 7:00 AM through 23:00 PM. BRM will be detuned.
4. The Advisory Module (AM) is running in the background and is accessed by the subject when they desire advice. When the advice button is pressed, the subject will be asked whether this is meal advice or correction advice. The subject will be required to request correction advice from the AM if the Hyperglycemia Red Light Alarm occurs. In that scenario, correction boluses may be suggested by the AM between those hours and must be confirmed by the study subject prior to injection. There is no limit on the number of times that a subject can request advice from the AM.
5. Breakfast will occur approximately 8:00 AM (between 07:00 and 08:30) and insulin administration will occur as described for all meals.
6. Lunch will occur approximately 12:00 PM (between 12:00 PM and 13:00 PM).
7. At approximately 14:00, the subject will be required to take a 45 minute walk or similar activity with staff. The subject may walk in the neighborhood near the hotel or guest house or inside the house but must be accompanied by medical personnel. During any walks, the system will be observed remotely by the study technician. Staff will carry hypoglycemia treatment supplies, including a glucagon emergency kit. Subjects will be permitted to snack before, during, or after the walk without insulin to prevent hypoglycemia.
8. Dinner will occur at approximately 19:00 PM (between 19:00 PM and 20:30 PM).
9. At 23:00, DiAs will detune the AM control. The SSM and the BRM will continue to run overnight and is responsible for lowering the basal rate or insulin delivery to avoid hypoglycemia or augmenting the basal rate to compensate for changes in insulin sensitivity overnight (e.g. dawn phenomenon).
10. At approximately 23:00, lights will be turned out, and the subject will be encouraged to sleep.
11. The staff will be checking the readings of the secondary CGM receiver at 03:00 AM and 05:00 AM during the night. Additional readings may be taken as necessary.
12. Remote monitoring of the subject will be active.

EXPERIMENTAL SESSION DAY 7:

1. The subject will be awakened shortly before 7:00 AM and allowed time for routine hygiene.
2. A fingerstick value will be obtained upon waking while the subject is still fasting.

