3. At 7:00 AM, the DiAs will stop AAA control. The system components (CGM sensors, study pump) will be removed.
4. The subject will resume his/her normal home pump therapy.
5. A fingerstick value will be obtained prior to discharge.
6. The subject will be discharged by approximately 9:00 AM if the following 3 conditions below are met:
 - a. the fingerstick value is 80-249 mg/dL
 - b. the glucose trend is stable
 - c. Insulin on Board is appropriate as determined by the MD
7. If the subject's glucose is out of the specified parameters, the Hypoglycemia or Hyperglycemia Safety Protocol will be followed until the subject is in the specified range.
8. Staff will request that subject remain at the Research House until approximately 9 AM so subject can be observed while eating breakfast.
9. Study staff will contact the subject within 24-48 hours after discharge.

5. Procedures During the Control session at Home (Days 5-7)

1. The study subject will start a new pump site on the morning of Day 5 to avoid initiation of a new site during the Control session at Home.
2. The study subject will follow the same schedule for timing of meals, snacks, exercise and bedtime as the experimental session.
3. The study subject will consume the identical meals and snacks as the experimental session. In the unlikely event, that the identical food is unavailable, the closest match of carbohydrate content will be chosen.
4. The study subject will administer insulin through their home insulin pump using their usual parameters.
5. Subjects will be allowed to use temporary basal rates at home.
6. The study subject will perform fingersticks using the study glucometer at a minimum at the identical scheduled times as the experimental session.
7. The subject will be instructed that all fingersticks should be preceded by hand washing with warm water and a dry towel. The subject will be instructed to obtain fingerstick, avoiding alternative sites, when obtaining blood values. The first drop of blood will be discarded. The second hanging drop will be used to measure the glucose level.
8. The subject will be reminded that all treatment decisions should be based on fingerstick values and not on CGM values.
9. The subject may take additional fingerstick readings as desired.
10. The subject will use the CGM throughout the study days with the hypoglycemia alarm set at 90 mg/dL and the hyperglycemia alarm set at 260 mg/dL. If either the CGM alarms, a fingerstick value will be obtained.

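### Food matching is written only from the experimental to the control session, so unplanned and preventive snacks are handled differently by sequence and can distort the SA1 contrast

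*Combined protocol and SAP*

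**What the plan says.** Section I.J (Endpoints) states that "the main study will have randomized cross-over design with each patient participating in two study weeks". Section I.G.3 confirms that both orders occur: "For those subjects who were randomized to the control session first, they will proceed as described in" the control-session procedures.

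The matching rules are these:

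- Section I.G.4, Meal Times During the Study: "Meals and snacks eaten during the experimental session will need to be exactly the same during the control session at home". The same list allows snacks between scheduled meals and an optional snack at 22:00-23:00. It also asks subjects to use the same carbohydrate information for dosing.
- Section I.G.5, item 2: "The study subject will follow the same schedule for timing of meals, snacks, exercise and bedtime as the experimental session".
- Section I.G.5, item 3: "The study subject will consume the identical meals and snacks as the experimental session". If the food cannot be obtained, "the closest match of carbohydrate content will be chosen".
- Section I.G.5, item 17: physical activity is to be comparable with the experimental session.

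Section I.G.4, Day 6, item 7 places a 45-minute walk at about 14:00 and adds: "Subjects will be permitted to snack before, during, or after the walk without insulin to prevent hypoglycemia".

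Sections I.C and I.L define the SA1 comparison over 14:00-19:00. Section I.J makes the Low BG Index associated with exercise the SA1 primary endpoint. Section I.L plans repeated measures ANOVA with contrasts and names no sequence or period term.

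**The concern.** Every matching rule takes the experimental session as the template and the control session as the copy. That works when the experimental session comes first. When the control session comes first there is nothing yet to copy, and nothing says that the experimental session must then reproduce the control session. The only fallback deals with food that cannot be obtained, not with session order.

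Two consequences matter for the comparison. First, food that is not planned is matched in one sequence and left open in the other. Second, the rule refers to what was eaten and makes no exception for carbohydrate taken to avert hypoglycaemia. A subject who snacked around the walk because glucose was falling under AAA control would, on a literal reading, eat the same snack on the control day whatever the glucose was then. SA1 measures hypoglycaemia risk in exactly that period, so the control result would partly reflect what happened under AAA.

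**Working it through.** The plan states no figure on this point to reproduce. The check sets the provisions side by side and then uses simple algebra to show where a distortion would go.

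**Step 1: what can be matched in either order**

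| Item | Source | Control first | Experimental first |
|---|---|---|---|
| Meal windows, walk at about 14:00, lights out at about 23:00 | I.G.4; timeline in I.B | Yes, set for everyone | Yes |
| Scheduled prepackaged meals and planned snacks | I.G.4; food report in I.G.5 item 16 | Feasible if fixed beforehand or repeated from the control report, but neither is stated | Yes |
| Unplanned snacks between meals; whether and what is eaten at 22:00-23:00 | I.G.4 | Cannot be copied; not yet chosen | Copied |
| Uninsulinised snacks around the walk | I.G.4 Day 6 item 7 | Cannot be copied; not yet eaten | Copied, on a literal reading |

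The gap is in the last two rows.

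**Step 2: overlap with the SA1 window.** The walk runs from about 14:00 to 14:45. A snack during or after it falls inside 14:00-19:00. A snack just before it falls outside the window but acts on glucose within it.

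**Step 3: effect on the contrast.** Let A and C be the mean SA1 outcome under AAA and control without copied preventive snacks. Let π be the period effect (period 2 minus period 1). Let b be the change in the control outcome of experimental-first subjects caused by the copied snacks. The within-subject differences (AAA minus control) are:

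- Experimental first: d1 = A − (C + b + π) = (A − C) − b − π
- Control first: d2 = (A + π) − C = (A − C) + π

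Averaging the two sequences with equal weight: (d1 + d2)/2 = (A − C) − b/2.

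Half their difference: (d1 − d2)/2 = −π − b/2.

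Apart from any period effect, the two sequences therefore estimate contrasts that differ by b, and the averaged contrast is off by b/2 in size. The second line shows that b is mixed with the period effect. Adding a period term would not remove the b/2.

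**Step 4: direction.** If the copied carbohydrate raises control-day glucose, the control Low BG Index falls and b is negative. A − C is negative if AAA works, and −b/2 is then positive, so the benefit of AAA on SA1 is understated.

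**Step 5: size.** The documents do not say how often walk snacks are eaten, how many grams they contain, how far they move the Low BG Index, or what the sequence allocation ratio is. For scale only, an assumed b of 0.1 to 0.3 SD in size shifts the averaged contrast by 0.05 to 0.15 SD and separates the sequences by 0.1 to 0.3 SD. The range is an assumption.

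**The case against.** The best defence is that most matching does not depend on order. The timetable is fixed for every subject, and staff stay in contact during the control days to keep time points consistent. On food, "Meals and snacks will be prepackaged meals purchased by the study team and will be brought in to the study site", and sameness is discussed with the subject in advance. Control-day meals and snacks are reported to staff as they occur, so a record exists that the experimental session could repeat. All of this stands. It limits the concern to unplanned and preventive snacks, plus an unstated rule for the control-first order.

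It can also be said that walk snacks were never meant to be part of the matched menu. The permission does not say that they are, and foods for treating hypoglycaemia are stocked separately. Control-day safety follows a home protocol in Appendix A-6, which is not among the documents. That may be the intention, but the matching rule covers snacks eaten and makes no exception, so the two provisions need to be reconciled.

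Recording is partly in place. Under DiAs training in Section I.H, subjects press a button after each roughly 16 g of glucose taken as hypoglycaemia treatment. That covers treatment. The text does not clearly extend it to preventive snacks, and no matching entry in grams is required on the control days.

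A reader might go further and infer that matching is impossible for control-first subjects, that half of the 36 completers cannot comply, and that power falls measurably. The documents do not support this. Planned food can be matched in either order, no allocation ratio is given, and not every subject need snack. A power loss also needs an assumed rise in the SD of paired differences. With 36 subjects, two-sided 0.01 and a paired t-test, the stated 85% for SA2 implies a standardised difference of 0.632. Raising the SD by 2% in half the subjects leaves 84%; raising it by 30% leaves 71%. The result is set by an input that has no source.

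**Conclusion.** The concern holds in limited form. The food-matching rule runs in one direction within a design that uses both orders. Followed as written, it treats unplanned snacks and uninsulinised walk snacks differently by sequence. In experimental-first subjects it can carry a response to glucose under AAA into the control day's SA1 window. The SA1 contrast can therefore be distorted and can differ between sequences, and the planned analysis would neither detect nor remove this.

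The size is unknown. It depends on how often such snacks are eaten and on whether staff apply the rule literally. The conclusion does not rest on an allocation ratio or a power calculation. It assumes that the appendices and Figure 2, which are not available, contain no reverse-order rule or exception. The point is worth correcting because it touches a primary endpoint and costs little to settle.

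**What to change.** In Section I.G.4 (Meal Times During the Study) and Section I.G.5 (items 2 and 3), make matching symmetric in one of two ways:

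- Fix one written menu before the first session, covering meals, planned snacks, carbohydrate entries and clock times, and use it in both sessions.
- State that the second session reproduces the first, whichever comes first.

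Reconcile the sameness rule with the walk-snack permission, so that carbohydrate taken in response to glucose is not part of the matched menu. This is needed under the second option as well; otherwise control-first subjects would carry control-day preventive snacks into the AAA session. Record the time and grams of such carbohydrate in both sessions and tabulate them by session and sequence.

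These changes affect matching and recording only. They do not alter when a subject may snack or be treated.

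The cost is a few protocol sentences, a menu sheet and one line on the food record. The study team already buys the food, and control-day intake is already reported to staff.
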